5.4 Trial procedures**5.4.1 Screening**

Patients considered unsuitable for inclusion in this trial should be identified by their Investigator before the end of their participation in the preceding trial (i.e. should the investigator feel participation in the long term safety study is not in the patient's benefit or if the patient declines to participate in AK581) allowing adequate time for any alternative therapy to be implemented. The Investigators should discuss the suitability of patients to enter AK581 with the Sponsor at least four weeks before the likely time of entry in order that documentation, including ICF, can be put in place and continuity of drug supply can be ensured.

Ideally the patient will be entered on the long term safety trial on the last day of dosing of the parent trial on condition that they have provided consent.

5.4.2 *Dosing period(s)*

Patients will be dispensed drug at suitable timepoints during the trial

5.4.3 *Exiting the trial*

Patients may choose to leave the trial at any time or may be withdrawn by the Investigator in case of lack of efficacy, adverse reactions to rVA576 (Coversin), lack of compliance or for any other reason which, in the opinion of the Investigator, makes their continued participation no longer in their best interests.

Patients will also leave this trial, or an extended access trial if one is required, once rVA576 (Coversin) is fully approved and reimbursed for their indication in their country and once continuity of supply has been ensured.

5.4.4 *End of Study/Follow-up*

All patients will have a follow up clinic visit at 1 Month \pm 7 days and all women of child bearing potential (WOCBP) will have a follow up visit at Month 3 \pm 7 days from last dose.

Table 8: Schedule of Events for PNH Patients

EVENT (PNH)	Entry	ⁱ 1 Months (±7 days)	2 Months (±7 days)	3 Months (±7 days)	6 Months (±7 days)	9 Months (±7 days)	12 Months (±7 days)	15 Months (±7 days)	18 Months (±7 days)	21 Months (±7 days)	24 Months (±7 days)
Medical History. Eligibility & Informed Consent & demographics	✓										
ⁱⁱⁱ Physical Examination if not done within 7 days of entry	✓	✓	✓	✓	✓	✓	✓	✓	✓	✓	✓
^{iv} Vital Signs (including weight) at every visit	✓ ^{vii}	✓	✓	✓	✓	✓	✓	✓	✓	✓	✓
^v ECG	✓ ^{vii}						✓				✓
Urinalysis (including pregnancy testing) ^{viii}	✓ ^{vii}	✓	✓	✓	✓	✓	✓	✓	✓	✓	✓
ⁱⁱ Haematology & Chemistry including LDH, FBC and creatinine (local or central labs)	✓ ^{vii}	✓	✓	✓	✓	✓	✓	✓	✓	✓	✓

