9.1 Statistical methods

A Statistical Analysis Plan (SAP) is in place. There will be no formal statistical inferences. All the study data will be analysed descriptively. Standard summary statistics will be produced for observed values, and changes from entry (where applicable) at the relevant post-entry timepoint.

For continuous variables, these statistics will include the number of patients with available data, mean, standard deviation, median, minimum, maximum. For categorical variables, these statistics will consist of patient counts and associated percentages. Unless otherwise specified, missing data will not be included in the denominator for percentage calculation. Time to event data will be summarised using graphs and summary statistics from the Kaplan-Meier method.

Listings will also be used to display data at the individual patient's level.

Data will be reported at each 3-month time point since the start of the study (where applicable) and over the entire period of the study (where applicable).

Results will be reported for all patients and then separately for PNH and aHUS patients.

- The incidence of AEs, and serious adverse events (SAEs) will be summarised over time for all patients.
- Vital signs, results of standard laboratory tests (clinical chemistry, haematology and urinalysis), and results of limb lead or 12 lead electrocardiograms (ECGs) will be summarised over time for all patients.
- The proportion of subjects with no adverse change in overall scores of Quality of Life using the EORTC QLQ-C30 (some PNH patients only), the EQ-5D-5L and FACIT-F instruments will be summarised over-time.

For PNH patients, additional summaries will include :

- The proportion of subjects with thrombotic and haemolytic event-free status
- The time to thrombotic or haemolytic event since entry.
- The time to first transfusion since entry.
- The proportion of subjects with serum Lactate Dehydrogenase (LDH) <1.8, >1.8 to 2.4, >2.4 to 3, and >3 times the upper limit of normal (ULN).

- The proportion of subjects with median serum Lactate Dehydrogenase (LDH) <1.8, >1.8 to 2.4, >2.4 to 3, and >3 times the upper limit of normal (ULN).
- The proportion of subjects who require PRBC transfusion.
- The proportion of transfusion independent subjects, with haemoglobin (g/L) above the baseline haemoglobin value they had at the start of the parent trial.

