This SAP only describes the analyses that will be performed for PNH patients given that the aHUS trial has been terminated due to inability to recruit. Therefore as no aHUS patients will enter AK581, all references to objectives and analyses related to aHUS patients have been removed from this SAP.

2 Study Objectives and Study Design

The objective of the trial is to provide a database of information regarding long-term administration of rVA576 (Coversin) to show that it remains safe for long periods and is acceptable to patients and show that the effect observed in the previous clinical trial is maintained. It also provides the opportunity to adjust an individual patient's dose or dose frequency should it be considered desirable. All patients enrolled into the CONSERVE study will have transitioned from a parent clinical trial.

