4.1 Changes from Protocol

- ADA analyses may be performed at a later stage and results will be reported separately from the main CSR.
- The LDH categories referenced in the protocol were < 1.8, >1.8 to 2.4, >2.4 to 3, and >3 times the upper limit of normal (ULN), given that these do not cover LDH equal to 1.8ULN, the following categories will be used serum LDH ≤ 1.8, >1.8 to 2.4, >2.4 to 3, and >3 ULN

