4.2 Analysis Sets

4.2.1 *Screened Set*

The Screened Set will include all patients screened for participation in the study.

4.2.2 *Full Analysis Set*

The primary analysis will be intention to treat and all patients who entered and signed informed consent will be included. The Full Analysis Set (FAS) will therefore include all enrolled patients.

All patients will be included in the safety analysis, whether completing the trial according to the protocol or not. Analyses of efficacy at various time points (6 months 12 months, 2, 3, 4 and 5 years) will be made for all patients reaching those points. The FAS will be the population used for assessing safety and efficacy and will be used for all outputs with the exception of patient disposition summary and data listings.

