4.11.1 Blood Transfusions

The proportion of subjects who require PRBC transfusion during each 3-month period since the start of the study and over the entire period of the study will be summarised. This summary will also be produced by subgroup of patients based on their transfusions and complement inhibitor history as defined in section 3.2.4.

The number of RBC or platelet transfusions per patient during the study will be summarised using descriptive statistics. Patients with no recorded transfusions will be included with an imputed count of zero.

The time (days) to first transfusion for each patient will be summarized using Kaplan-Meier methodology. Kaplan-Meier estimates of the proportion of patients receiving at least one transfusion during the study will be displayed with 95% two-sided confidence limits. The median, 95% Confidence Interval of the median, 25th and 75th percentiles of the time to first transfusion will be produced.

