4.12.1 Adverse Events

A summary overview of adverse events will be provided, which presents the number and percentage of patients from the FAS satisfying each of the following categories:

- Any AEs
- Serious AEs (SAEs)
- Drug-related AEs
- SAEs leading to death
- AEs leading to discontinuation

The number and percentage of patients with AEs, and number of AEs will be summarised by MedDRA System Organ Class, High Level Term, and Preferred Term. In this summary, any patient reporting multiple episodes of the same AE (i.e. same preferred term), will be counted once. The incidence of SAE will also be summarised. The listings will contain all data available.

The number and percentage of patients with AEs will be summarised by reported severity within each preferred term within system organ class. In this summary, any patients reporting multiple episodes of the same AE (i.e. same preferred term), will be counted once against the most severely reported category.

A list of patients reporting any SAEs and a list of patients reporting any AEs that led to an interruption or withdrawal of the study medication will be provided.

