4.12.5 Thrombotic and Haemolytic Events

The number and percentage of patients

- i) without a thrombotic event,
- ii) without a haemolytic event,
- iii) without either a thrombotic or haemolytic event,

will be summarized at each visit. The time (days) to first event for each patient will be summarized using Kaplan-Meier methodology. Kaplan-Meier estimates of the proportion of patients achieving each event during the study will be displayed with 95% two-sided

confidence limits. The median, 95% Confidence Interval of the median, 25th and 75th percentiles of the time to achieving event will be produced.

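### Protocol 9.1 promises AE and SAE incidence over time, but SAP 4.12.1 plans only whole-study counts and percentages, which under unequal follow-up mix risk with duration

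*Protocol*

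**What the plan says.** AEs and SAEs come first in the primary endpoint (SAP 2.4.1), and the stated aim is "to show that it remains safe for long periods" (SAP 2). Protocol 9.1 sets this summary: "The incidence of AEs, and serious adverse events (SAEs) will be summarised over time for all patients". Its next bullet uses the same phrase for vital signs, laboratory tests and ECG, which SAP 4.12.2 to 4.12.4 summarise mainly by visit.

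For AEs the core sentence of SAP 4.12.1 is: "The number and percentage of patients with AEs, and number of AEs will be summarised by MedDRA System Organ Class", followed by lower MedDRA levels. The section adds an overview, SAE incidence and maximum severity. None of these has a period or a number at risk, and the titles of Tables 14.3.1.1 to 14.3.1.4 add none. The denominator is the FAS, that is, all enrolled patients (SAP 4.2.2).

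Elsewhere the SAP does set a time frame:

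- SAP 4.11.1: "The proportion of subjects who require PRBC transfusion during each 3-month period since the start of the study and over the entire period".
- SAP 4.12.5, for patients free of thrombotic or haemolytic events: "will be summarized at each visit. The time (days) to first event for each patient will be summarized using Kaplan-Meier methodology".
- SAP 4.2.2, for those reaching each point: "Analyses of efficacy at various time points (6 months 12 months, 2, 3, 4 and 5 years) will be made". This covers efficacy only.

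SAP 4.1 lists two changes from the protocol. One is "ADA analyses may be performed at a later stage and results will be reported separately from the main CSR"; the other concerns the LDH categories.

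**The concern.** Follow-up will be unequal. Treatment lasts up to 4 years (Protocol 5.3), and "Patients may choose to leave the trial at any time or may be withdrawn by the Investigator" (Protocol 5.4.3). The SAP 4.9 exposure bands start at 1-182 days.

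In a crude FAS percentage, a patient who left after three months counts in the denominator as fully as one followed for four years. The percentage therefore lies below the risk over the full treatment period and changes when follow-up alone changes. It can also come out the same for a constant and a rising rate. A long-term safety study exists to describe what happens late, and this figure does not show that by itself. The gap concerns AEs and SAEs in general, including infection. Thrombotic and haemolytic events and MAVEs already have Kaplan-Meier summaries.

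**Working it through.** **Text.** The protocol asks for AE and SAE incidence over time. The SAP gives AE and SAE incidence with no time element and does not list the change. The plan has no AE rate, power or sample-size figure to reproduce.

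**Inputs.** From the documents: N about 50, up to 4 years of treatment, and the four SAP exposure bands. Assumed, because the documents give none: event rates and the spread of follow-up. Two follow-up patterns are used.

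- A: uniform over 0 to 4 years. Total 100 person-years (PY), 75 before and 25 after year 2; 25 patients reach year 2.
- B: a quarter of patients spread evenly within each SAP band (0-0.5, 0.5-1, 1-2, 2-3 years). Total 62.5 PY, 56.25 before and 6.25 after year 2; 12.5 patients reach year 2.

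**Formula.** Crude percentage = average over follow-up T of 1 − exp(−H(T)), where H is the cumulative hazard. Risk to time t = 1 − exp(−H(t)).

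**1. Effect of follow-up alone, constant rate.** In A the formula is 1 − (1 − e^(−4λ))/(4λ). With λ = 0.06 this is 1 − 0.2134/0.24 = 11.1%.

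| Rate per 100 PY | Crude, A | Crude, B | 3-year risk |
|---|---|---|---|
| 2 | 3.9% | 2.5% | 5.8% |
| 5 | 9.4% | 6.0% | 13.9% |
| 6 | 11.1% | 7.1% | 16.5% |
| 10 | 17.6% | 11.4% | 25.9% |

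At 6 per 100 PY the 4-year risk is 1 − e^(−0.24) = 21.3%.

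**2. Rising against constant rate, matched on expected events.** The rising rate is 4, then 12 per 100 PY from year 2.

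- A: expected events are 0.04 × 75 + 0.12 × 25 = 6.0, equal to 0.06 × 100. Crude is 10.9% (rising) and 11.1% (constant). The 4-year risks are 1 − e^(−0.32) = 27.4% and 21.3%.
- B: expected events are 0.04 × 56.25 + 0.12 × 6.25 = 3.0, equal to 0.048 × 62.5. Crude is 5.7% for both. The 3-year risks are 1 − e^(−0.20) = 18.1% and 1 − e^(−0.144) = 13.4%.

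The matching is deliberate. A different total would move the crude figure (a constant 4 gives 7.6% in A). Because events are matched, one overall rate (total events over total exposure) would not separate the two patterns either.

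**3. What a by-period table would show in A.** Patients starting a period at year a: 50 × (1 − a/4). PY between a and b: 50 × [(b − a) − (b² − a²)/8]. Expected events: rate × PY.

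| Months | At risk at start | PY | Events, constant 6 | Events, 4 then 12 |
|---|---|---|---|---|
| 0-6 | 50 | 23.4 | 1.4 | 0.9 |
| 6-12 | 43.75 | 20.3 | 1.2 | 0.8 |
| 12-24 | 37.5 | 31.25 | 1.9 | 1.25 |
| 24-36 | 25 | 18.75 | 1.1 | 2.25 |
| 36-48 | 12.5 | 6.25 | 0.4 | 0.75 |

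One SAE after year 2 adds 1/50 = 2% to the planned table. It is 1/25 = 4% of those reaching year 2 in A and 1/12.5 = 8% in B.

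**4. Precision.** In A, 3 events in 75 PY is 4.0 per 100 PY (exact 95% CI 0.8 to 11.7), and 3 in 25 PY is 12.0 (2.5 to 35.1). The exact test of 3 of 6 events falling in the last 25% of PY gives p = 0.17. With no events after year 2, the upper limit is 3.689/25 = 14.8 per 100 PY in A and 3.689/6.25 = 59.0 in B.

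**The case against.** **The denominator can be rebuilt.** A reader might infer that the planned safety outputs as a whole cannot show how many patients were still on drug when late events occurred. The documents do not support that. N minus the lower bands of the SAP 4.9 exposure table gives the number with exposure beyond about 6, 12 and 24 months, interruptions aside. Under the assumptions above it returns the 25 (A) and 12.5 (B) for year 2. Listings of AEs, exposure, visit dates and disposition are planned as well (SAP 7.2). This objection stands, and it reduces the gap to the lack of any planned output that puts events and patients at risk together.

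**The protocol version is uncertain.** A reader might also infer that the SAP silently dropped a commitment. The SAP is based on version 3.0 (SAP 1), and the version of the supplied protocol cannot be seen. The evidence points both ways. The protocol LDH categories that SAP 4.1 cites match the supplied Protocol 9.1, but those in SAP 2.4.2 differ from the supplied Protocol 3.2.1. The mismatch between the two supplied texts is a fact; its cause is unknown.

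**The wording is loose.** The protocol does not define the time frame, and the table shells sit in a stand-alone document (SAP 6). Table titles alone settle little: those of 14.3.5.1 and 14.3.5.2 omit the by-visit element that SAP 4.12.5 requires. For AEs, however, the SAP text supplies no time element either.

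**The study is descriptive and small.** This is true. No decision rule changes, and SAEs are reported within 24 hours (Protocol 7.3) with annual safety reports (Protocol 7.5). But the missing item is itself a descriptive table.

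**Conclusion.** The point holds as a modest gap between protocol and SAP on the AE part of the primary endpoint. On their own, the planned AE and SAE percentages mix risk with duration and cannot separate a constant rate from a rising one. In the illustrations the crude figure falls well below the longer-term risk (7.1% or 11.1% against a 3-year risk of 16.5% at 6 per 100 PY), and patterns whose long-term risks differ by 5 to 6 percentage points look alike.

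Every rate and follow-up pattern here is assumed, so these numbers show the mechanism and do not predict the trial. N may also be below 50, since the SAP now covers PNH patients only.

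It would be wrong to infer that a by-period table would settle whether risk rises. The p = 0.17 and the wide limits above show that it would not. Time would also run from CONSERVE entry in patients already treated in a parent trial. Late periods would hold a selected group, because entry requires clinical benefit and exit is free.

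**What to change.** In SAP 4.12.1, add one descriptive table of any AE, SAE and AE leading to discontinuation by period since CONSERVE entry: 0-6, 6-12, 12-24, 24-36 and 36-48 months. These cut points follow those in SAP 4.2.2 for efficacy. Show patients at risk at the start of the period, patients with an event, number of events and person-years.

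State in the text that time runs from CONSERVE entry and not from the first rVA576 dose in the parent trial. State also that late periods hold few, selected patients, so the table describes a pattern and cannot prove or exclude a rise.

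In SAP 4.9, add an exposure band above 1095 days. The bands stop at 3 years while treatment may last 4, so exposure in the last period has no row of its own.

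Rates per 100 person-years with exact Poisson intervals and a serious-infection row go beyond the Protocol 9.1 promise. They are optional and would be exploratory, in line with SAP 3.7. If no over-time AE summary is intended, say so in SAP 4.1 with the reason.

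The cost is one paragraph, one table and one extra band, built from AE and dosing dates already collected. The drawback is sparse late rows that a reader could over-interpret, which the statement above is meant to prevent.

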9.2 Number of patients

This is an open-label study to evaluate the safety experience of long term rVA576 (Coversin) treatment in approximately 50 patients.

9.3 Interim analyses

The Sponsor reserves the right to review accruing safety and efficacy data from the study as a management aid to assist in the design of future studies.

9.4 Assessment of pharmacokinetics and complement activity

Blood (5mL) samples for CH50 assays and rVA576 (Coversin) levels will be collected according to the schedule presented in **Table 8 & Table 9**. Serum samples will be taken to measure complement activity, rVA576 (Coversin) levels and anti-drug antibodies. Blood-EDTA and blood-citrate will be used for other measures. Safety blood samples will take precedence over all other procedures.

PK parameters will be described over-time using summary statistics and lines and mean plots as appropriate.

PD parameters will be described over-time using summary statistics and graphical displays such as waterfall plots and lines plots as appropriate.

9.5 Significance level

All analyses will be descriptive.

9.6 Missing, unused or spurious data

Missing data that cannot be retrieved from source records or other repositories will be recorded as such in the eCRFs and will not be entered into the statistical analysis. Spurious data will be examined by the Sponsor's monitor, medical or statistical advisors and a decision made as to how it should be handled. If there is an obvious transcription or data entry error, such as a misplaced decimal point in a biochemical parameter, this will be discussed with the CRO or the laboratory and, if all parties agree, it will be corrected and endorsed by both the PI and the Sponsor.

Unused data (e.g. superfluous blood pressure recordings or haematological results in addition to those required by the protocol) will remain part of the source documentation and only be incorporated into the trial documents and analysis if there is reason for them to be (e.g. an unexpected fall in blood pressure that might constitute an AE).

9.7 Deviation from the statistical analysis plan

It is not envisaged that there should be any deviations from the SAP. Any unexpected deviations will be included in any interim reports and the Final Study Report.

9.8 Patients to be included in the statistical analysis

The primary analysis will be intention to treat (ITT) and all patients entered and who sign informed consent will be included.

All patients will be included in the safety analysis, whether completing the trial according to the protocol or not. Analyses of efficacy at various time points (6 months, 12 months, 2, 3, 4 and 5 years) will be made for all patients reaching those points.

‘End of study’ will be defined as the point at which the last patient has exited the study and has been seen at the 3 month end of study follow-up visit.

The final analysis will be performed using data collected up to the end of the study. This data will be presented in a Final Study Report.

The Database will be locked when the last patient last follow-up visit occurs.

10 Quality Control and Assurance

The hospitals / departments taking part in the trial are responsible for maintaining their own SOPs and QA / QC procedures. The Sponsor or their delegate will also implement and maintain quality control and quality assurance procedures with written standard operating procedures (SOPs) to ensure that the study is conducted and data are generated, documented and reported in compliance with the Protocol, ICH GCP and all applicable regulatory requirements. The Sponsor or delegate will be responsible for monitoring the trial and carrying out 100% source data verification. The Sponsor will be responsible for overseeing clinical trial activities.

The study will be in accordance with the provisions of the Declaration of Helsinki and all revisions thereof, in accordance with ICH GCP and as required by applicable regulatory requirements.

Any necessary training for the study will be provided to Investigators and study personnel by the Sponsor or their designee prior to study initiation.

11 Ethical Conduct of the Study

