6.2 Withdrawal criteria

In accordance with applicable regulations, a patient has the right to withdraw from the study at any time and for any reason, without prejudice to their future medical care by the physician or at the Institution. Should a patient withdraw from the study, then the patient will not undergo any further study-specific procedures or receive any treatment mandated by the protocol.

If a subject fails to attend scheduled trial assessments, the Investigator must determine the reasons and the circumstances as completely and accurately as possible.

In the event of the premature withdrawal of a patient from the trial, the end of trial visit should be carried out as completely as possible. Minimally, a safety assessment should be performed.

In the case of withdrawal due to the occurrence of unacceptable toxicity, the patient will be requested to remain under the supervision of the Investigator until the toxicity has resolved or is no longer considered to be clinically significant by the Investigator.

If an Adverse Event classified as severe results in patient withdrawal from the study, the subject will be followed until the AE (or SAE) resolves or stabilises, and any interventions required to resolve or stabilise the event will be recorded in the eCRF.

All withdrawals must be documented in the eCRF. A patient may be withdrawn in any of the following circumstances.

- Withdrawal of consent (mandatory withdrawal)
- Intake of non-permitted concomitant medication (may be discussed with the Sponsor and dependent on the nature of the medication)
- Patient is non-compliant with more than three consecutive missed doses and two missed clinic visits, in the opinion of the Investigator (discretionary withdrawal)
- If discontinuation is considered necessary by the Investigator and/or Sponsor (mandatory withdrawal)
- Request of Regulatory Agency (mandatory withdrawal)
- Patient develops an illness that would compromise his participation in the study (may be discussed with sponsor)
- Patient is not achieving complete inhibition at the maximum assigned dose (inadequate response to rVA576 (Coversin) treatment)
- Pregnancy, unless the patient wishes to consent to a termination.

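### Visit-wise LDH and quality-of-life proportions, on the most natural reading, drop patients who left for lack of efficacy, so they can make the effect look better maintained than it is

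*Protocol*

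**What the plan says.** Protocol 3.1 gives as one aim of the study to show that the effect seen in the parent trial is maintained. SAP 4.11.2 reports the share of patients in each LDH category by 3-month period. SAP 4.11.5 to 4.11.7 report, by 3-month period, the share with no adverse change on QLQ-C30 global health status, EQ-5D-5L and FACIT-F.

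Four provisions bear on who is in those percentages:

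- Protocol 9.1: unless something else is specified, "missing data will not be included in the denominator for percentage calculation".
- Protocol 9.6, repeated in SAP 4.3: missing data that cannot be retrieved "will be recorded as such in the eCRFs and will not be entered into the statistical analysis".
- Protocol 9.8 and SAP 4.2.2: efficacy analyses at 6 months, 12 months and the later yearly points "will be made for all patients reaching those points".
- SAP 4.2.2: "The FAS will be the population used for assessing safety and efficacy and will be used for all outputs", except patient disposition and listings. The FAS is all enrolled patients.

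On leaving the study, Protocol 5.4.3 says patients "may be withdrawn by the Investigator in case of lack of efficacy". Protocol 6.2 lists among its withdrawal circumstances: "Patient is not achieving complete inhibition at the maximum assigned dose". Patients also leave once the drug "is fully approved and reimbursed for their indication in their country". SAP 4.6 summarises the primary reason for withdrawal in the disposition output.

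**The concern.** A table headed Full Analysis Set suggests a percentage of everyone who entered. If patients who have left drop out of the denominator, it is a percentage of those who stayed, which answers a narrower question. Staying is not independent of the outcome, because loss of control is itself a ground for withdrawal. Entry already requires clinical benefit and sustained CH50 inhibition (Protocol 4.1), so the starting group is selected for response, and later loss of control is what these tables need to show. The study has no comparator and no formal inference, so a reader judging whether the effect lasted has little beyond these percentages over time.

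**Working it through.** The documents give no exit rate, no distribution of exit reasons and no expected control rate, so there is no planned figure to reproduce. The check has two steps.

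**Step 1: what happens to a patient who has left.** At visits after exit there is no LDH or quality-of-life value. The patient could be dropped, have a last value carried forward, or be counted as not maintained. Protocol 9.1, 9.6 and SAP 4.3 provide for dropping. The derivations in SAP 3.3.2 and 3.3.4 to 3.3.6 and the analyses in SAP 4.11.2 and 4.11.5 to 4.11.7 provide neither of the others. Where the SAP wanted a rule for patients without records it wrote one: SAP 4.11.1 sets the transfusion count to zero for patients with none recorded. The FAS label says who may enter a table, and Protocol 9.1 sets the base of the percentage.

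**Step 2: effect on the percentage.** Let m be patients with a value at the visit, s those controlled, p = s/m, and e the patients who left earlier for lack of efficacy or inadequate response.

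- Observed-case proportion: s/m.
- Proportion counting those exits as not maintained: s/(m + e).
- Difference: p × e/(m + e).

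*Assumed example.* N = 50 (the approximate planned number), 20% leave (10), half of them for lack of efficacy (e = 5), and 80% of the remaining 40 are controlled (s = 32). Observed-case: 32/40 = 80.0%. Counting the 5: 32/45 = 71.1%. Difference: 0.80 × 5/45 = 8.9 points.

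*Assumed range.* Exit 10% to 40%, 25% to 100% of exits for lack of efficacy, 60% to 80% controlled among those remaining:

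- Smallest: m = 45, e = 1.25, p = 0.60, so 0.60 × 1.25/46.25 = 1.6 points.
- Largest: m = 30, e = 20, p = 0.80, so 0.80 × 20/50 = 32 points.
- With e = 0 the difference is 0.

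*Drift with no change in control.* Suppose 30 of 50 patients are controlled throughout and only uncontrolled patients leave:

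| Uncontrolled patients who left | Observed-case | Exits counted |
|---|---|---|
| 0 | 30/50 = 60.0% | 30/50 = 60.0% |
| 5 | 30/45 = 66.7% | 60.0% |
| 10 | 30/40 = 75.0% | 60.0% |
| 15 | 30/35 = 85.7% | 60.0% |
| 20 | 30/30 = 100% | 60.0% |

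*Leavers who are not failures on the endpoint.* If only a share f of the e patients are failures on LDH or quality of life, the overstatement is [e/(m + e)] × [p − (1 − f)]. With m = 40, e = 10, s = 36, the observed figure is 36/40 = 90%. With f = 1 the proportion over all 50 is 36/50 = 72% (18 points lower). With f = 0.5 it is 41/50 = 82% (8 points lower). The overstatement is zero if leavers succeed as often as stayers.

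*Opposite direction.* If a share a leaves as responders, for example on drug approval, the proportion among all who entered is 0.90(1 − a) + a: 0.91 at a = 0.10 and 0.92 at a = 0.20. The observed 90% then understates by 1 to 2 points.

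**The case against.** The strongest reply has four parts.

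*The reaching-those-points sentence does not govern the 3-month tables.* This is correct. It names 6 months, 12 months and the yearly points. For the 3-month tables the argument rests on Protocol 9.1, 9.6 and SAP 4.3, and 9.1 is a default that can be overridden. The SAP does not restate it, and table shells and derived-data specifications are in separate documents (SAP 6). Denominators could be settled there, so the conditional denominator is the most natural reading, not a certainty.

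*Loss of control would often be seen before exit.* This also stands in part. An inadequate response leads first to consideration of a dose increase. Protocol 5.2 words this as mandatory and 5.9 as discretionary; the two need reconciling. Values during that phase enter the tables. On premature withdrawal "the end of trial visit should be carried out as completely as possible", and Protocol Table 8 schedules LDH and the questionnaires at Early Termination. But no rule assigns those values to a 3-month period or keeps the patient in later ones.

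*Other outputs show it.* Whole-study median LDH categories, individual LDH plots, listings and the disposition table all help. Kaplan-Meier outputs use each patient's follow-up to exit. None of the tables in SAP 7.1 joins exit reasons to the visit-wise proportions.

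*The study is descriptive with a safety primary endpoint.* This is true, and it limits the consequence to secondary results.

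A reader might go further and infer that the planned figures will be biased upwards by a known amount. The documents do not support that: every rate above is assumed, and the direction can reverse. Nor do they show that the transfusion and event-free proportions share the problem. Their denominators are not stated, and a patient who has left could be treated there as missing or as event-free.

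**Conclusion.** The point holds in a limited form. On the most natural reading of Protocol 9.1, 9.6 and SAP 4.3, with Protocol 9.8 and SAP 4.2.2 for the 6-month, 12-month and yearly analyses, the visit-wise LDH-category and no-adverse-change quality-of-life proportions are conditional on still being in the study. Patients who leave for lack of efficacy or inadequate response drop out of later denominators, so these proportions can stay flat or rise without any better control.

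The size cannot be determined from the documents. It is zero without such exits, and 1.6 to 32 points over the assumed range if every such exit is counted as a failure. It is smaller where some of those who leave are still controlled on the endpoint. The primary safety endpoint and the Kaplan-Meier outputs are not called into question. It would also be wrong to infer that every exit should count as failure: deaths, exits on drug approval and late entry say nothing of that kind. This is a cheap improvement to the plan, not the correction of an invalid analysis.

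**What to change.** Keep the observed-case tables and print n at each visit. For LDH ≤1.8 × ULN and for each quality-of-life no-adverse-change proportion, add one sensitivity table beside them, clearly labelled:

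- **Denominator at each visit:** patients with an observed value, plus patients who left earlier for lack of efficacy or inadequate response and whose entry date would have let them reach that visit. The second group counts as not maintained.
- **Outside the denominator, in separate rows with n and reason:** deaths, exits on drug approval, other exits, and patients not yet at that visit.
- **QLQ-C30:** restrict to patients assigned that instrument, since only some PNH patients complete it.
- **Early Termination values:** state to which 3-month period they are assigned.
- **Kaplan-Meier analyses:** leave the event definitions unchanged, so that withdrawal does not become an event.

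The cost is SAP wording and a few tables. The primary withdrawal reason is already planned for summary (SAP 4.6), but its categories are not listed. Check that lack of efficacy and inadequate response can be identified from it. The maintenance figures will look less favourable. The added table is a conservative bound, because an inadequate response on complement inhibition is not always an LDH or quality-of-life failure. That is why both versions should be shown side by side.
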